### 3.1.3 Tertiary objectives and endpoints

Tertiary objective	Endpoint
[REDACTED]	[REDACTED]
[REDACTED]	[REDACTED]
[REDACTED]	[REDACTED] [REDACTED] [REDACTED] [REDACTED]

[figure not shown]
### 3.2 Design of the clinical trial

This is a first in man, open label, multi-centre Phase I trial to investigate the safety, immunogenicity and patient survival when administered the DC vaccine, AST-VAC2, in patients with advanced NSCLC (metastatic or locally advanced disease).

All enrolled patients will receive AST-VAC2 to establish if the vaccine can be delivered with an acceptable safety profile and to investigate immune response in peripheral blood, [REDACTED] See Figure 2.

Safety review and stopping rule criteria are detailed in [Section 3.3](#). The study data will undergo independent review if stopping rule criteria are met. Staggered patient recruitment will be employed in order for emerging safety data to be reviewed before further patients are recruited ([Section 3.3.2](#)).

Figure 2. Overall Trial design

## CONFIDENTIAL

All potential patients will be asked to consent to a pre-screening assessment of HLA typing. Only patients who are screened and found to be HLA A\*02:01 positive will be asked to consent to the main trial and continue into screening to establish eligibility for trial treatment.

It is expected that up to eight patients will be recruited, the final number depending on the emerging safety data, patient replacement and vaccine availability.

Patients will receive six AST-VAC2 vaccinations (administered by two id injections for each vaccination), once a week (every 7 days +/- 1 day) for six weeks. Only one target dose of AST-VAC2 will be explored i.e.  $1 \times 10^7$  cells. A reduced dose of AST-VAC2 or a reduction in number of vaccinations administered, may be considered following observation of unacceptable toxicity at this dose level. Any modification to the vaccination dose/schedule will be determined and agreed by the Sponsor & Chief Investigator based on emerging data as the trial progresses.

The 'End of Trial' will be declared once all patients have either withdrawn (see Section 11.0) from the trial or died, or the last patient has completed their final safety follow-up visit (5 years post the first vaccination), whichever is the latter.

### 3.3 Safety Review

#### 3.3.1 Safety considerations

AST-VAC2 has never been investigated in the clinic so no clinical safety data are available. Based upon experience with other autologous and allogeneic DC vaccines, including AST-VAC1, the potential toxicities of AST-VAC2 are expected to be minimal. Severe AEs related to AST-VAC1 (related autologous DC cell therapy, Section 2.4 and IB section 5.1.2.1) have not been observed in Phase I and II clinical trials with the possible exception of an occurrence of thrombocytopenia in one patient with acute myeloid leukaemia (AML).

The principal potential toxicity of AST-VAC2 is likely to be related to the allogeneic nature of the AST-VAC2 vaccine which could lead to injection site inflammation. However, it is noted that the mixed leucocyte reaction could elicit an adjuvant effect which may be beneficial in the context of this trial. Systemic inflammatory responses associated with cytokine release have not been demonstrated in dendritic cell vaccines to date and therefore are not considered to be a significant risk for AST-VAC2.

Chronic toxicities, particularly related to unintended proliferation of AST-VAC2, are not anticipated. AST-VAC2 is derived from a hESC line. The cells are terminally differentiated during manufacture to generate cells with a phenotype comparable to that of autologous dendritic cells, which are known to have a low proliferative potential and a short biological half-life. Furthermore, these cells are irradiated post-cryopreservation to minimise the risk of any cells with proliferative potential remaining in the IMP. Finally, AST-VAC2 is only partially haplotyped to the recipient therefore the recipient may also induce a rejection reaction to the cells causing rapid elimination. Overall, the drug product is therefore expected to have no proliferative potential in vivo and the potential for tumourgenicity/ectopic growth is considered to be remote.

All AEs observed during this trial will be assessed using NCI CTCAE Version 4.02, with the exception of Injection Site Reactions (ISR) which are defined using the protocol specific grading system detailed in [Section 9.8](#).

The risk of developing any of the AEs noted above and in [Section 3.3.3](#) is low and largely theoretical however if any of the above is seen or suspected during the vaccination schedule or follow up period, investigators should investigate as per standard clinical practice and may include assessments as appropriate. If any of these AEs meet the stopping rule criteria as set out in [Section 3.3.3](#), this will trigger an independent review as stated.

[figure not shown]
#### 3.3.2 Safety Evaluation

Only one target dose level is being explored in this trial.

## CONFIDENTIAL

Safety evaluations by the Sponsor and collaborating Investigators will be conducted after the first patient has received AST-VAC2 and then again after the second and third patients have been treated, Figure 4. Once open recruitment has been initiated, safety review will be performed at regular intervals (as required).

**Figure 3. Safety Evaluation**

A safety review committee, consisting of all Investigators, representatives of the Sponsor and representatives of the drug company (observers only), will review emerging study data (to include all clinical data, safety data listings and applicable PD data) on an ongoing basis, with particular reference to ensuring that patients are able to complete the vaccination schedule without AST-VAC2 toxicity-related delays. Should the committee have significant concerns about toxicity seen during the trial they will have the authority to suspend or terminate the trial and/or make recommendations to the Sponsor to modify the vaccination administration.

Pending discussions between the Sponsor and CI and based on vaccine availability, the following options may be considered during the trial:

- Reduced dose and/or
- Modified number of vaccinations, e.g. if plateaued immune responses are observed with fewer vaccinations in those patients already treated.

### 3.3.2.1 Data to be discussed at safety review meetings.

Data which should be discussed at the safety review meeting will include:

- Patients treated since the last safety review meeting including vaccine related adverse events noted and duration of treatment.
- Assessment and agreement on any related adverse events that may have occurred and resulting actions.
- Relevant PD data available since the last meeting.
- Any additional relevant information relating to adverse events or patient safety which may have arisen following distribution of listings for the meeting and will therefore not be documented in the listings.
- Any possible concern after the review of cumulative data e.g. toxicities.
- Assessment and agreement on continuation of patient enrolment to the study.

### 3.3.3 Stopping rule criteria.

On observation of any of the following related adverse events, the study data (defined above) will be reviewed by the independent Protocol Safety and Review Board (PSRB) for an opinion.

- ISR Grade 3 or 4 (as per protocol specific grading system).
- Clinically significant systemic allergic reaction (in the judgement of the investigator)
- Evidence of clinically significant autoimmunity (in the judgement of the investigator)
- Cytokine release syndrome Grade 3 or 4.
- Evidence of tumorigenicity/ectopic growth (including teratoma formation).
- Any other clinically significant toxicity (in the judgement of the investigator)

## CONFIDENTIAL

Any incidences of the related adverse events detailed here must be reported to the Sponsor as a medically important serious adverse event (SAE) (see [Section 9.2.2](#)).

### 3.4 Patient evaluability

#### 3.4.1 Response

All patients who meet the eligibility criteria, receive at least one AST-VAC2 vaccination, have a baseline assessment and at least one repeat assessment of measurable disease will be evaluable for response. Response is not a primary endpoint however patients will be assessed for any potential responses to trial treatment. Disease will be measured according to the modified Immune-related Response Criteria (irRC) ([Appendix 3](#)).

#### 3.4.2 Safety

All patients who meet the eligibility criteria and receive at least one administration of AST-VAC2 will be evaluable for the assessment of the primary endpoint of safety.

#### 3.4.3 Immunogenicity

Patients will be defined as “immune evaluable” for the secondary immunogenicity endpoints if the criteria below are met:

- Has received at least three scheduled AST-VAC2 vaccinations (three vaccinations have been shown to be adequate to measure a peripheral immune response) and;
- Has provided a baseline research blood sample plus samples at two subsequent sampling time points. Every effort should be made to collect the sample 2 weeks after the last vaccination (Section 8.0) and/or

[REDACTED]

[REDACTED]

If no immune response is seen at the three month time point, later time points may not be analysed. If the patient consents, any remaining samples not yet analysed will be considered a research ‘gift’ before future research is performed on the sample.

## 4 PATIENT SELECTION

### 4.1 Eligibility criteria

The patient must fulfil the eligibility criteria (listed in Sections 4.1.1 and 4.1.2).

#### 4.1.1 Inclusion criteria

1. Patients with advanced NSCLC (metastatic or locally advanced), for whom there are no other suitable treatment options –
  - Able to and likely to be well enough to receive six vaccinations i.e. judged by the Investigator to not require alternate treatment for the duration of the vaccination schedule and period to end of vaccination visit.
  - Has had sufficient wash out periods from previous treatments as follows:
    - i) four weeks for chemotherapy
    - ii) six weeks for investigational medicinal products (IMPs)
    - iii) eight weeks for immunotherapy (shorter intervals may be acceptable based on half-life of treatment. Eligibility will be confirmed by the Sponsor and CI).
  - Measurable disease
  - Biopsiable disease is preferable however patients without biopsiable disease can still be considered for the study.
2. Written (signed and dated) informed consent and be capable of co-operating with treatment and follow-up.
3. Confirmed HLA A\*02:01 positive genotype.
4. Life expectancy of at least 12 weeks.
5. World Health Organisation (WHO) performance status of 0-2.
6. Haematological and biochemical indices within the ranges shown below. These measurements must be performed prior to the patient receiving the first AST-VAC2 vaccination.

Laboratory Test	Value required
Haemoglobin (Hb)	≥9.0 g/dL
Absolute neutrophil count (ANC)	≥1.5 x 10  /L
Platelet count	≥100 x 10  /L
Lymphocyte count	≥1.0 x 10  /L
Bilirubin	≤1.5 x upper limit of normal (ULN)
Alanine aminotransferase (ALT) or aspartate aminotransferase (AST) and alkaline phosphatase (ALP)	≤ 3.0 x ULN
Calculated creatinine clearance	> 30 mL/min

7. 18 years or over at the time consent is given.

#### 4.1.2 Exclusion criteria

1. Radiotherapy (except for palliative reasons) during the previous four weeks before treatment.
2. Ongoing toxic manifestations of previous treatments greater than CTCAE Grade 1. Exceptions to this are alopecia or certain Grade 2 toxicities, which in the opinion of the Investigator should not exclude the patient. If there is uncertainty over whether the toxicity should exclude the patient, the Sponsor should be consulted.

## CONFIDENTIAL

3. Systemic steroids or other drugs with a likely effect on immune competence are forbidden during the trial with the exception of replacement treatment. Inhaled and topical steroids are permitted. The predictable need of their use will preclude the patient from trial entry.
4. Female patients who are able to become pregnant (or are already pregnant or lactating). However, those patients who have a negative serum or urine pregnancy test before enrolment and agree to use two forms of contraception (one effective form plus a barrier method) [oral, injected or implanted hormonal contraception and condom; intra-uterine device and condom; diaphragm with spermicidal gel and condom] or agree to sexual abstinence\*, effective from the first administration of AST-VAC2 throughout the trial and for six months afterwards are considered eligible.
5. Male patients with partners of child-bearing potential (unless they agree to take measures not to father children by using a barrier method of contraception [condom plus spermicide] or to sexual abstinence\* effective from the first administration of AST-VAC2, throughout the trial and for six months afterwards. Men with partners of child-bearing potential must also be willing to ensure that their partner uses an effective method of contraception for the same duration for example, hormonal contraception, intrauterine device, diaphragm with spermicidal gel or sexual abstinence). Men with pregnant or lactating partners must be advised to use barrier method contraception (for example, condom plus spermicidal gel) to prevent exposure of the foetus or neonate.
6. Major thoracic or abdominal surgery from which the patient has not yet recovered.
7. At high medical risk because of non-malignant systemic disease including active uncontrolled infection.
8. Known to be serologically positive for Hepatitis B, Hepatitis C or Human Immunodeficiency Virus (HIV).
9. Evidence of any ongoing active autoimmune disease.
10. Concurrent congestive heart failure, prior history of class III/ IV cardiac disease (New York Heart Association [NYHA]), prior history of cardiac ischaemia or prior history of cardiac arrhythmia.
11. Is a participant or plans to participate in another interventional clinical trial, whilst taking part in this Phase I trial of AST-VAC2. Participation in an observational trial or interventional clinical trial which does not involve administration of an IMP and which would not place an unacceptable burden on the patient in the opinion of the Investigator and Medical Advisor would be acceptable.
12. Any vaccination given within four weeks before the first AST-VAC2 vaccination (except for COVID-19 vaccinations, which are permitted at the Investigator's discretion).
13. Any planned prophylactic vaccination from trial entry until completion of the AST-VAC2 vaccinations (except for planned COVID-19 vaccinations, which are permitted at the Investigator's discretion).
14. Any condition which might interfere with the patient's ability to generate an immune response.
15. Any other condition which in the Investigator's opinion would not make the patient a good candidate for the clinical trial.

\* Abstinence is only considered to be an acceptable method of contraception when this is in line with the preferred and usual lifestyle of the subject. Periodic abstinence (e.g., calendar, ovulation, symptothermal, post-ovulation methods) and withdrawal are not acceptable methods of contraception.

## **4.2 Patient enrolment**

Before enrolling the patient in the trial, the Investigator or designated representative should determine the eligibility of the patient during the trial screening period. Please ensure that the Sponsor is notified of any eligibility concerns at least four working days before treatment is planned.

Eligible patients must be enrolled in the electronic data capture (EDC) system by site staff and then registered by the Sponsor before they start treatment with AST-VAC2.

Eligible patients will be allocated a trial number by the EDC system during the enrolment process. The Sponsor will send confirmation of the patient registration and dose level, to the investigator following enrolment of the patient; trial treatment may only be administered after this confirmation has been received.

## 5 TREATMENT

### 5.1 Selection of the Phase I clinical dose and schedule

The therapeutic vaccine will be administered via two intradermal (id) injections at a target dose of  $1 \times 10^7$  cells on each vaccination day. The actual cell dose patients may receive will vary, up to a maximum of  $2 \times 10^7$  viable cells, to achieve a target dose of  $1 \times 10^7$  viable cells – Section 6.2.5 for further details on dose.

The dose of AST-VAC2 has been selected based on previous clinical experience with autologous dendritic cells (DCs) [REDACTED] in which a dose of  $1 \times 10^7$  cells was shown to induce anti-hTERT T cell responses in patients with either prostate cancer or AML.

### 5.2 Dosing schedule/treatment schedule

Patients will receive six AST-VAC2 vaccinations, administered by id injection weekly over a period of six weeks. An interval of 7 days (+/-1 day) should occur between each of the vaccination days. The target total administered dose of vaccine is  $1 \times 10^7$  cells of AST-VAC2 which will be administered as two id injections for each vaccination.

AST-VAC2 vaccine will be given by id injection in the deltoid muscle of the arm, the outer thigh surface, anterior abdominal wall or buttock. If an injection site reaction (ISR) has resolved after the first vaccination /previous vaccination days then for subsequent injections, injections can be administered at the same body site. If an ISR from a previous vaccination is still present ( $\geq$ Grade 1) then the injections should be administered into an alternative site.

Only one dose of AST-VAC2 will be explored in this trial. A reduced dose/administration schedule may be considered as per [Section 3.3](#) based on emerging safety data.

### 5.3 Enrolment

Initially, one patient will be recruited and will receive their first four vaccinations before the second and third patients are recruited. It is acceptable for these next patients to receive treatment in parallel. The second and third patients must receive their first four vaccinations before recruitment is opened to the remaining patients.

Safety evaluations by the Sponsor and collaborating Investigators ([Section 3.3](#)) will be conducted after the first patient has received AST-VAC2 and then again after the second and third patients have been treated. Once open recruitment has been initiated, safety review will be performed at regular intervals (as required).

#### 5.3.1 Dose reductions

Pending discussions between the Sponsor and Chief Investigator (CI) and based on vaccine availability, the following options may be considered during the trial:

- Reduced dose and/or
- Modified number of vaccinations, e.g. if plateaued immune responses are observed with fewer vaccinations in those patients already treated.

#### 5.3.2 Dose delays & interruptions

If at the time of the next scheduled vaccination day, one or more adverse events (AEs) (excluding ISRs) related to the AST-VAC2 vaccine (highly probably, probably or possibly related) are still present, have not resolved to Grade  $\leq 1$  and are considered by the Investigator to be clinically significant and a clear contraindication to vaccination, the next vaccination day should be delayed for up to two weeks until the AE(s) have recovered to this level. In case of uncertainty, individual cases should be discussed with the Sponsor. Patients who require a dose interruption of greater than two weeks will be reviewed on a case by case basis to determine whether the patient should be withdrawn from the trial. The Sponsor will confirm whether an extended interruption is acceptable or if the patient should be withdrawn from further trial treatment.

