### 1.4 Trial Design:

This is a first in man, open label, multi-centre Phase I trial to investigate the safety, immunogenicity and patient survival following administration of the dendritic cell (DC) vaccine AST-VAC2 in patients with advanced NSCLC (metastatic or locally advanced).

All enrolled patients will receive AST-VAC2.

Safety review and stopping rule criteria are detailed in [Section 3.3](#). If stopping criteria are met as per protocol, this will trigger an independent review of the data. Pharmacodynamic data will also be reviewed as available.

All potential trial patients will be asked to consent to a pre-screening assessment of Human Leucocyte Antigen (HLA) typing. Once the HLA result is known, patients who are HLA A\*02:01 positive will be asked to consent to participate in the main trial. Patients who are HLA A\*02:01 negative will not be eligible for the trial.

[figure not shown]
Patients receiving AST-VAC2 will be followed up for safety (primary endpoint), pharmacodynamic analyses in blood samples (secondary endpoint) [REDACTED].

All patients will be followed up for up to two years post first vaccination for overall survival and for five years post first vaccination for safety.

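### Grade 3-4 injection site reactions are stopping-rule events, yet they are excluded from the dose-delay rule and no default hold is written while the review board's opinion is pending

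*Protocol*

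**What the plan says.** **Delay rule.** Protocol 5.3.2 applies when, at the next vaccination day, "one or more adverse events (AEs) (excluding ISRs) related to the AST-VAC2 vaccine" persist above Grade 1 and the Investigator considers them clinically significant and a clear contraindication. The dose is then put back by up to two weeks, and longer interruptions go to the Sponsor case by case. The treatment-compliance text of the SAP repeats the ISR exclusion. The version history shows that Amendment 01 introduced the exclusion as a clarification. The visible text gives no reason for applying it to the top grades.

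**Site rule.** Protocol 5.2 and 6.2.5 say that if an ISR of Grade 1 or above remains, the injections go to a different body site. No upper grade is set.

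**Stopping rule.** Protocol 3.3.3 lists six related events, among them "ISR Grade 3 or 4 (as per protocol specific grading system" and "Cytokine release syndrome Grade 3 or 4". When any of them is seen, the study data "will be reviewed by the independent Protocol Safety and Review Board (PSRB) for an opinion", and the event is reported as an SAE. Three other places describe the same consequence: 1.4 ("If stopping criteria are met as per protocol, this will trigger an independent review of the data"), 3.2 ("The study data will undergo independent review if stopping rule criteria are met") and 3.3.1 ("this will trigger an independent review as stated").

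**Grading and default course.** Under 9.8, a Grade 3 ISR is tissue damage severe enough to call for an operation, and Grade 4 is life-threatening. Under 5.4, vaccination continues to six doses unless a listed exception applies.

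**The concern.** This is a first-in-human allogeneic cell product. Section 3.3.1 names its allogeneic nature, which could inflame the injection site, as the likely source of its principal toxicity. The protocol treats a severe local reaction as serious enough for independent review, but its dosing rules treat ISRs of all grades alike. The patient who has just had such a reaction is due another dose about a week later, and the dosing instruction written specifically for ISRs is to inject elsewhere.

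What is at stake is whether that patient's next dose waits for the review. If the text sets no default, the decision is made under time pressure, by judgement, in a multi-centre trial.

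**Working it through.** There is no figure in the plan to reproduce. The check is a side-by-side reading plus interval arithmetic.

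**1. Which stopping-rule events does the delay rule reach?**

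| Trigger in 3.3.3 (related events) | Covered by the delay rule in 5.3.2? | Hold pending the PSRB opinion in visible text? |
|---|---|---|
| ISR Grade 3-4 | No, excluded at every grade | None found |
| Systemic allergic reaction | Conditionally | None found |
| Autoimmunity | Conditionally | None found |
| Cytokine release syndrome Grade 3-4 | Conditionally | None found |
| Tumorigenicity or ectopic growth | Conditionally | None found |
| Other clinically significant toxicity | Conditionally | None found |

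Conditionally means that the event is still above Grade 1 at the next dosing day and the Investigator judges it clinically significant and a clear contraindication. None of the four places that state the consequence of a trigger (1.4, 3.2, 3.3.1, 3.3.3) mentions the affected patient's next dose.

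**2. Two cases walked through the text.**

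- *Grade 3 ISR, still present at the next visit.* The adverse-event check before each vaccination (7.2) would pick it up. The delay rule does not apply. Sections 5.2 and 6.2.5 point to another site. Section 5.4 continues treatment unless someone decides that toxicity is unacceptable or that the patient should stop. Section 3.3.3 has started a review but is silent on the dose.
- *Grade 3 cytokine release syndrome, resolved before the next visit.* The delay rule applied in principle, but its condition of an unresolved event is no longer met. The review is under way and the dose is not held.

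**3. Time available.** Inputs: a dosing interval of 7 days plus or minus 1 (5.2) and an SAE report within 24 hours of site awareness (9.4).

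- Next dose due: 7 − 1 = 6 to 7 + 1 = 8 days after the last.
- Event recognised on the vaccination day and reported at the limit: 6 − 1 = 5 to 8 − 1 = 7 days remain for an opinion.
- Event recognised d days after the dose: 5 − d to 7 − d days remain. With d = 3 as an illustration, that is 2 to 4 days.

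The documents give no turnaround time for the PSRB, so whether its opinion would come before the dose cannot be determined.

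**4. Room in the existing rule.** A delay of up to 14 days beyond the due date ends 6 + 14 = 20 to 8 + 14 = 22 days after the last dose. A hold could run that long before the Sponsor's existing review of extended interruptions is needed.

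**The case against.** The strongest reply is that dosing can already be stopped by several routes. Section 5.4 ends vaccination for unacceptable toxicity or on the Investigator's decision, and a Grade 3 or 4 ISR plausibly qualifies. Section 5.3.2 invites discussion with the Sponsor in uncertain cases. The Sponsor and Chief Investigator may change dose or schedule (3.2), and the safety review committee may suspend the trial (3.3.2, 13.4). Urgent safety measures need no prior authorisation (9.6). Every trigger is reported as an SAE within 24 hours, so the Sponsor should normally know before the next dose, and a committee that includes all Investigators limits variation between sites. All of this stands. Each route is a power to act, however, and none is a default attached to a trigger. By contrast, 5.3.2 does write a plain delay to keep 48 hours between this vaccine and a COVID-19 vaccine.

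A reader might infer that the protocol requires redosing after a severe ISR. It does not. The site instruction says where to inject if a dose is given, delay is not forbidden, and the SAP expects delays and omissions. A reader might also infer that no trigger has any written dosing action. That is too strong, because 5.3.2 delays the five non-ISR triggers while they are unresolved and judged a clear contraindication.

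Staggered entry (5.3) does not answer the point, since it governs when later patients are recruited.

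Finally, the design and safety-evaluation figures are not reproduced and might show a hold. That possibility remains open.

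**Conclusion.** The point holds for the visible text, most clearly for the ISR trigger. A related Grade 3 or 4 ISR has neither a written delay rule nor a default hold before a dose due 6 to 8 days after the last. For the other five triggers the gap is narrower: an event that settles within the week, or is not judged a clear contraindication, is not held while the PSRB considers it.

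The size in patients or doses cannot be stated. The documents give no rate of Grade 3-4 ISRs and no PSRB turnaround. Section 3.3.1 expects toxicity to be minimal and up to eight patients are planned, so few should be affected. The conclusion assumes that the omitted figures show no hold. This is a cheap improvement to patient safety wording and does not affect the planned analyses.

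**What to change.** - **5.3.2 and the matching SAP sentence:** restrict the ISR exclusion to Grades 1 and 2.
- **5.2 and 6.2.5:** restrict the alternative-site instruction to ISRs of Grades 1 and 2.
- **3.3.3:** add that after any related stopping-rule event the affected patient receives no further vaccination until the PSRB has given its opinion, and that holds beyond two weeks go to the Sponsor review already described in 5.3.2.

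Both parts are needed. Narrowing the exclusion alone would still leave a Grade 3 ISR to the Investigator's contraindication test; only the sentence in 3.3.3 creates a default. The exclusion remains for the mild reactions it can reasonably cover. The hold concerns the affected patient only. Dosing of other patients and enrolment stay with the safety review committee unless the Sponsor chooses to add a rule for them.

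The cost is wording in four protocol sections and one SAP sentence, through the usual amendment process, with no added patients or procedures. The downside is a possible delayed or missed dose in a rare patient, and a Sponsor review if the opinion is slow.
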